## 6.1.3. Protocol Deviations

Important protocol deviations will be summarized.

Protocol deviations will be tracked by the study team throughout the conduct of the study. These protocol deviations will be reviewed to identify those considered as important as follows:

- Data will be reviewed prior to unblinding and freezing the database to ensure all important deviations (where possible without knowing the study intervention details) are captured and categorized in the protocol deviations dataset.
- This dataset will be the basis for the summaries of important protocol deviations.

## 6.1.4. Prior and Concomitant Medications

Concomitant medications (CM) will be coded using the WHO Drug dictionaries. Summaries of the number and percentage of participants taking concomitant medications will be displayed by ingredient only (not by ATC classification). These summaries will include single-ingredient medications and will present multi-ingredient medications according to the combination of the component ingredients. Separate summaries will be produced for those medications taken pre-, during, and post-treatment.

**Pre-Treatment:** CM Start Date < Study Treatment Start Date

**On-Treatment (During):** If CM Start Date < Study Treatment Start Date and CM Stop Date >= Study Treatment Start Date

Or

If Study Treatment Start Date < CM Start Date < Last Dose of Study Treatment Date + 182 days

**Post-Treatment:** If CM Start Date < Last Dose of Study Treatment Date + 182 days

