6.8.1. Permitted CRSwNP and Asthma Medications

The following medications may be used for all participants:

Short courses of systemic corticosteroids (for example of systemic corticosteroids for treatment of CRSwNP) are permitted prior to Screening and after Randomization, but not during the Run-in period. Although the use of rescue medications such as systemic CS is allowable during the treatment phase of the study (Visit 2 and onwards); the date and time of rescue medication administration as well as the name

26 Jun 2024 78

- Protocol Amendment 5 Final
- and dosage regimen (dose and duration) of the rescue medication must be recorded in the eCRF for NP as well as for other comorbidities.
- 2. Throughout the study, asthmatic participants are to be maintained on their baseline SoC asthma treatment.
- 3. Courses of antibiotics and saline nasal douches are permitted at any time. For antibiotic treatment for CRSwNP / ECRS, the type, dose and duration must also be recorded in the eCRF.
- 4. INCS are allowed with no interruption throughout the study duration. If a participant in Japan is not on INCS prior to screening, the participant is permitted to start INCS during the study, if required for symptom management. Once on INCS, the participant should remain on INCS for the remainder of the study.

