## 6.3.2. Study Period

Assessments and events will be classified according to the time of occurrence relative to the study intervention period.

**Pre-treatment** is defined as time prior to the first dose of study intervention.

Assessment/Event Date ≤ Study Treatment Start Date

**On-treatment** is defined as time from first dose to last date plus 182 days.

Study Treatment Start Date < Assessment/Event Date ≤ Date of Last Dose of Study Treatment + 182 days

**Post-treatment** is defined as any time post on-intervention window, i.e. > last dose date plus 182 days.

Assessment/Event Date > Date of Last Dose of Study Treatment + 182 days

Assessments collected on the date of randomization, for which there is no time of assessment will be considered pre-intervention.

Assessments will be considered on-treatment if the assessment start date is missing.

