History	Missing start day	If study intervention start date is missing (i.e. participant did not start study intervention), then set start date = 1st of month.	
		Else if study intervention start date is not missing:	
		If month and year of start date = month and year of study intervention start date, then	
		If stop date contains a full date and stop date is earlier than study intervention start date, then set start date= 1st of month.	
		Else set start date = study intervention start date.	
		Else set start date = 1st of month.	

Element	Reporting Detail		
	Missing start day and month	If study intervention start date is missing (i.e. participant did not start study intervention), then set start date = January 1.  Else if study intervention start date is not missing:  If year of start date = year of study intervention start date, then  If stop date contains a full date and stop date is earlier than study intervention start date, then set start date = January 1.  Else set start date = study. intervention start date.  Else set start date = January 1.	
	Missing end day	A '28/29/30/31' will be used for the day (dependent on the month and year).	
	Missing end day and month	A '31' will be used for the day and 'Dec' will be used for the month.	
	Completely missing start/end date	No imputation	

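### SAP 6.1.4 leaves medicines started on the first dose date, or exactly 182 days after the last dose, out of the on-treatment concomitant-medication summary

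*SAP*

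**What the plan says.** SAP 6.1.4 promises separate concomitant-medication summaries for the pre-treatment, on-treatment and post-treatment periods and defines each by dates.

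- Pre-treatment: "CM Start Date < Study Treatment Start Date".
- On-treatment, first branch: "If CM Start Date < Study Treatment Start Date and CM Stop Date >= Study Treatment Start Date".
- On-treatment, second branch: "If Study Treatment Start Date < CM Start Date < Last Dose of Study Treatment Date", where the upper limit is then moved on by 182 days.
- The line printed for the post-treatment period reads: "If CM Start Date < Last Dose of Study Treatment Date + 182 days".

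Two other SAP sections bear on these rules. Section 6.3.2, which classifies assessments and events, ends the on-treatment period with a closed bound: "Assessment/Event Date ≤ Date of Last Dose of Study Treatment + 182 days". It places the treatment start date itself in pre-treatment. Section 6.3.6 allows imputed dates to be used to assign records to study phases. For concomitant medications with a partial start date in the month (or, if the month is also missing, the year) of first dose, it first checks for a full stop date before first dose. If there is none, the instruction is "Else set start date = study intervention start date". Partial end dates are imputed to the end of the month or of the year. A completely missing end date is not imputed, and no rule is given for a medicine recorded as ongoing.

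**The concern.** The periods should between them give every dated record a sensible home. As printed they do not. The first dose date is excluded from pre-treatment by one strict sign and from on-treatment by another, and the imputation rule then moves records of uncertain date onto that same day. Starts on that day are plausible in their own right: medication is reviewed at Visit 2, and Protocol 6.8.1 permits rescue systemic corticosteroids from that visit.

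The closing day has a similar gap, and there the rule also disagrees with 6.3.2.

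At stake are the counts and percentages in the on-treatment table, which readers use to compare permitted and prohibited medication between the arms.

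**Working it through.** The plan states no figure for this rule, so there is none to reproduce. The check puts test records through the printed rules.

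**Inputs.** First dose is Day 1. The second dose is at Week 26, nominally Day 26 × 7 + 1 = 183 (SAP 4.5.1; study-day convention in SAP 6.3.3). Write E for last dose + 182 days.

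- Two doses: E = 183 + 182 = Day 365. This is nominal Week 52 (52 × 7 + 1 = 365) and the last diary day of Weeks 49–52 in SAP Table 2.
- One dose: E = 1 + 182 = Day 183, nominal Week 26.

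**Printed tests for a medicine with start s and stop t.**

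- Pre: s < 1.
- On: (s < 1 and t >= 1) or (1 < s < E).
- Post as printed: s < E. Post with the direction reversed: s > E.

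| Record | Pre | On | Post as printed | Post with > | Same date under 6.3.2 |
|---|---|---|---|---|---|
| s = Day 1, true or imputed | no | no | yes | no | pre |
| s = E − 1 | no | yes | yes | no | on |
| s = E | no | no | no | no | on |
| s = E + 1 | no | no | no | yes | post |
| s = Day 2, no stop date | no | yes | yes | no | on |
| s = Day −60, t = Day 365 | yes | yes | yes | no | not compared |
| s = Day −60, stop blank and treated as failing | yes | no | yes | no | not compared |
| s = Day −60, t = Day −5 | yes | no | yes | no | not compared |

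Each row gives the same answers for E = 365 and E = 183.

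**Day 1.** The start fails s < 1 and also fails s > 1. As printed, the record lands only in post-treatment, which cannot be intended, because that line catches nearly everything begun before E and nothing begun after it. With the direction corrected, the record has no period at all. The first on-treatment branch counts a medicine begun earlier and stopped on Day 1 as on-treatment, so 6.1.4 itself treats use on Day 1 as use during treatment.

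**Imputation.** A start known only to the month of first dose could truly be any day in that month, and one known only to the year any day in that year. Unless a full stop date precedes first dose, both are set to Day 1 and fall into the gap.

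**Upper end.** s = E fails s < E and also fails s > E. Section 6.3.2 makes the same date on-treatment.

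**Ongoing medicines.** Only the first branch uses a stop date, so a medicine begun on Day 2 is captured without one. A medicine begun before Day 1 with a recorded or imputed end on or after Day 1 is captured too. Only a wholly blank stop date is left without a stated outcome.

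**The case against.** The strongest reply is that both boundary points turn on < against ≤. A ≤ can be lost when a document is converted, and the printed post-treatment line already shows that the signs in this section cannot all be taken at face value. This stands as a reason to check the source PDF, but it does not rebut the point: the same section prints >= in the first branch, and ≤ appears in 6.3.2. If the source does show closed signs, the two boundary gaps disappear; the reversed post-treatment direction and the silence on ongoing medicines remain.

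It can also be said that leaving Day 1 out of on-treatment agrees with 6.3.2. That is correct. The fault is that 6.1.4 leaves Day 1 out of pre-treatment as well.

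A reader might go further and infer that all ongoing background intranasal corticosteroid (INCS) use drops out of the on-treatment table. Protocol 6.8.1 says "INCS are allowed with no interruption throughout the study duration", and outside Japan daily INCS must predate screening by at least 8 weeks, so only the first branch can capture it. The documents do not support that inference. The loss would need ongoing records to carry a blank stop date and a program that fails them. Neither is stated, Protocol 6.8 asks for end dates, and SAP 6.1 refers these summaries to company data standards that are not part of the plan.

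Nor do the documents show that every medicine started at the Week 52 visit is missed. Visits have a ±7-day window, and only a start falling exactly on last dose + 182 days is affected.

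**Conclusion.** The rule is wrong as written, on a small scale. One date at each end of the on-treatment period is mishandled for each participant: Day 1, together with the partial start dates imputed to it, and last dose + 182 days, where 6.1.4 contradicts 6.3.2. The number of records cannot be estimated, because the documents give no rates of Day 1 starts or of partial dates. The conclusion assumes that the printed signs match the source PDF. The Day 365 figure also assumes that the second dose is given on nominal Day 183.

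The ongoing-medicine point is a missing rule, not a demonstrated loss of data.

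The effect stops at descriptive concomitant-medication tables. SAP 4.2.1 handles the start of a disease-modulating medicine by the date of that event, not by the 6.1.4 periods. INCS use at baseline and important protocol deviations are summarised separately (SAP 6.1.2 and 6.1.3). No endpoint, estimand or test uses this rule.

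**What to change.** Check the comparison signs in 6.1.4 against the source PDF. Then restate the periods as follows.

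- **On-treatment (i):** start < treatment start and stop >= treatment start, with a medicine recorded as ongoing counted as continuing.
- **On-treatment (ii):** treatment start <= start <= last dose + 182 days.
- **Post-treatment:** start > last dose + 182 days, written out explicitly. It should not be defined as whatever is not on-treatment, because that would label a medicine ended before Day 1 as post-treatment.

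Add a note that a Day 1 start counts as on-treatment for medications although 6.3.2 treats Day 1 assessments as pre-treatment, so that the difference is deliberate and visible.

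Applied to the test records, starts on Day 1 (true or imputed) and on last dose + 182 days become on-treatment, and a start on last dose + 183 days becomes post-treatment only. The cost is a few lines of SAP wording and a small change to the derivation program. No new data are needed.

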#### 4.5.1. Extent of Exposure

Two doses of study treatment will be administered during study treatment period: the first at randomisation Visit 2 (Week 0) and the second at Visit 10 (Week 26). Each dose is viewed as providing therapeutic coverage for 26 weeks (182 days). The number of treatments administered, and the number of days exposure will be summarised descriptively and listed. Total subject-year exposure will also be presented.

Number of days of exposure to study treatment will be calculated as follow:

Duration of Exposure in Days = (Date of Final Dose) - (Date of First Dose) + 182 days (regardless of study withdrawal or death)

Subject years exposure is calculated as follow:

Subject Years Exposure = ((Date of Final Dose) – (Date of First Dose) + 182)/365.25

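### The SAP's post-treatment rule for concomitant medications points the wrong way around last dose + 182 days, contradicting the SAP's own study-period definition

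*SAP*

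**What the plan says.** SAP 6.1.4 states that "Separate summaries will be produced for those medications taken pre-, during, and post-treatment" and then gives a date rule for each period:

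- Pre-treatment: "CM Start Date < Study Treatment Start Date".
- On-treatment, for medication carried over from before the first dose: "If CM Start Date < Study Treatment Start Date and CM Stop Date >= Study Treatment Start Date".
- On-treatment, for medication started later: the start must fall strictly after the first-dose date and strictly before the cut-off of 182 days past the last dose.
- Post-treatment, the rule at issue here: "If CM Start Date < Last Dose of Study Treatment Date + 182 days".

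SAP 6.3.2 classifies assessments and events by the same three periods. Its prose says that post-treatment "is defined as any time post on-intervention window, i.e. > last dose date plus 182 days", and its formula is "Assessment/Event Date > Date of Last Dose of Study Treatment + 182 days". The 182 days come from SAP 4.5.1, which treats each dose as covering 26 weeks.

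**The concern.** The post-treatment line in 6.1.4 repeats the upper limit of the on-treatment line above it and has no lower limit. It therefore describes the time up to the end of the treatment window, not the time after it. A programmer or independent validator who follows the text would produce a post-treatment table filled with earlier medications. Medications started once treatment cover had ended would be shown nowhere.

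Those later medications are collected by design. Protocol 7.1 encourages participants who stop treatment to remain to Week 52. Footnote e of the Schedule of Activities (Protocol 1.3) places a follow-up contact with a medication review 30 weeks after the last dose for participants who withdraw. At stake is the accuracy of the medication-use tables in the study report, in particular what people took after their treatment cover had lapsed.

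**Working it through.** The SAP gives no figure to reproduce here, so the check is to apply the printed rules to start dates.

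**Inputs.** Nominal doses are on Day 1 and, at Week 26, Day 1 + 182 = Day 183 (Protocol Table 1). The window is 182 days after the last dose (SAP 4.5.1, 6.1.4 and 6.3.2). The follow-up contact is at 30 weeks = 210 days after the last dose (Protocol 1.3, footnote e). Write F for the first-dose date, L for the last-dose date and S for the medication start date.

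**Overlap.** A pre-treatment start has S < F. Since F ≤ L, it follows that S < L + 182, so the post-treatment rule is met. The carry-over on-treatment clause also requires S < F, so the same holds. The other on-treatment clause requires S < L + 182 directly. Every medication in the pre- or on-treatment summary therefore also enters the post-treatment summary.

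**Omission.** If S > L + 182, the pre-treatment rule fails, both on-treatment clauses fail, and the post-treatment rule fails. The medication is in no summary.

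**Both doses given.** L = 183, so the cut-off is 183 + 182 = Day 365. Follow-up at 30 weeks is 183 + 210 = Day 393. The start days after the cut-off are 366 to 393, which is 393 − 365 = 28 days. The printed rule captures 0 of 28.

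**Second dose missed, participant stays to Week 52.** L = 1, so the cut-off is 1 + 182 = Day 183. The start days from 184 to 365 number 365 − 183 = 182. The printed rule captures 0 of 182.

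With the 6.3.2 direction, S > L + 182, all 28 and all 182 start days are captured, and no pre- or on-treatment start enters.

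**Boundary days, as printed:**

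| Start date | SAP 6.1.4 pre- or on-treatment | SAP 6.3.2 formulas |
|---|---|---|
| S = F | neither | pre-treatment |
| S = L + 182 | neither | on-treatment |

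As printed, S = F meets only the reversed post-treatment rule, and S = L + 182 meets no rule. If the post-treatment sign alone is corrected, both dates fall outside all three periods. The first case is not remote, because SAP 6.3.6 sets some partial medication start dates to the first-dose date.

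**The case against.** **It may be a printing or conversion fault.** Some comparison signs in the SAP copy are plainly damaged, for example in the age categories of the subgroup table in 4.10.1. A lost bar could turn ≤ into <, so the boundary-day point must be checked against the original. It would not reverse a direction, however. A greater-or-equal sign survives within 6.1.4, and a greater-than sign survives in 6.3.2.

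**Not every early start would be misplaced.** Section 6.1.4 speaks of medications taken in a period, and its on-treatment rule carries ongoing medication forward. A nasal steroid used throughout could fairly be described as also taken post-treatment. That stands: it would be too strong to say that every such entry is wrong. But the printed rule has no stop-date condition, so it also admits courses that ended before the first dose. It still loses the later starts.

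**The programmed rule may already be right.** SAP 6.1 refers to the sponsor's data standards, and SAP 4.1.1 refers to a programming specification. Neither is available here, so it cannot be said that the final tables will be wrong. The SAP rule is still wrong as a specification.

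**A reader might infer damage to the primary estimand,** because steroids and biologics define intercurrent events. The documents do not support that. SAP 4.2.1 assigns worst scores from the date of the first intercurrent event and makes no use of the 6.1.4 period labels.

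**A reader might also infer that the on-treatment rule should simply include the first-dose date.** The 6.3.2 formulas place that date in pre-treatment. The accompanying prose is less clear, since it describes pre-treatment as before the first dose and on-treatment as from the first dose. The SAP does not settle the matter.

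**Conclusion.** The point holds for the direction of the post-treatment rule. SAP 6.1.4 and 6.3.2 contradict each other, and only the 6.3.2 direction fits a 182-day treatment window and three distinct summaries. As written, all starts before the cut-off enter the post-treatment table and all starts after it leave every table. The omission matters mainly for Weeks 26 to 52 in participants who miss the second dose but remain in the study. For participants given both doses it concerns only follow-up after Week 52. The day counts assume nominal dosing dates, and the 28-day figure assumes that the 30-week contact takes place.

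The consequence is confined to descriptive medication tables. No primary or secondary efficacy result depends on the rule. The boundary-day gaps are a lesser matter and are conditional on the signs being printed as intended.

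**What to change.** In SAP 6.1.4, change the post-treatment rule to CM Start Date > Last Dose of Study Treatment Date + 182 days.

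Then check the remaining signs in the original and align the boundary days with 6.3.2, so that every start date falls in a category. If the 6.3.2 formulas are kept, the first-dose date goes to pre-treatment, with the carry-over clause using the same sign, and last dose + 182 days goes to on-treatment. If the sponsor prefers to count the first-dose date as on-treatment, 6.3.2 must change as well.

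If medications continued past the window are also meant to appear as post-treatment, say so with a stop-date clause; the sign change alone does not provide this.

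The direction fix is one character. The boundary alignment is a few equality signs and a check of the programming specification. No data collection, sample size or efficacy analysis changes.

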# 6.2. Appendix 2 Electronic Clinical Outcome Assessment (eCOA) Compliance

The compliance of eCOA data (e.g., assessments collected via electronic patient diary cards) will be derived at the study-level (overall) and at the endpoint-level across all participants and by treatment group.

An eCOA will be considered complete if there is no missing data within the assessment.

## 6.2.1. Study-Level (Overall) Compliance

The study-level (overall) compliance for all eCOA assessments collected in the study will be assessed for all participants at all time-points between baseline through to the date of the participant's study completion or withdrawal. If an eCOA is only assessed for a certain sub-population, the compliance for only that sub-population will be included in the compliance calculation (i.e. ACQ-5 only administered in participants with asthma). The list of eCOA assessments that comprise the study-level (overall) compliance include all eCOA assessments collected within the study: VRS, VAS, Nasal Obstruction VAS, SNOT-22, PGIS, PGIC, ACQ-5, SF-36, and WPAI-GH.

The analyses related to the ACQ-5 endpoint are described in the pooled SAP, but are included in the compliance metrics for completeness.

The target overall compliance for the study is 70%.

Overall eCOA compliance (across all eCOAs and all participants) for the study is calculated as:

 $\frac{\textit{Total number of complete eCOAs across all participants}}{\textit{Total expected number of complete eCOAs across all participants}} \times 100$ 

Expected number of complete eCOAs

$$= \sum_{i=1}^{n} \sum_{j=1}^{c} data \ points \ expected \ for \ eCOA_{j}(participant \ i)$$

where c represents the total number of eCOAs collected and n represents the total number of participants.

For daily diary data this means every day is a data point in the denominator. For visit-based endpoints, each visit is a data point in the denominator. The study-level (overall) compliance metric will be summarized by treatment group and total across treatment groups.

A supplemental overall compliance metric will also be calculated for the study. The supplemental calculation will be based on an interval-based definition for daily diary data that is defined within Section 6.3.4.2 for a four-week interval result to be non-missing in the analysis. The number of data points in the denominator for the interval-based definition becomes the number of four-week time periods that are assessed, including the baseline assessment. Participants are considered compliant for the daily diary endpoints if

the appropriate number of non-missing values for each interval per the criteria described in Section 6.3.4.2. The denominator for the visit-based endpoints will remain the same. For visit-based endpoints, participants are considered compliant if they complete the assessment at that visit. This calculation will only include the eCOA endpoints in the multiplicity hierarchy: VRS, SNOT-22, and ACQ-5.

Both the study-level compliance and the supplemental overall compliance will be summarized at the participant level by pre-defined ranges for compliance (<40%, 40-<60%, 60-<80%>=80%). These will be summarized by treatment group and total across treatment groups.

